Kanglaite Reduce the Toxicity of Radiotherapy of Head and Neck Cancer Phase II Study

NCT03101514

January 6, 2017

Study Protocol and Statistical Analysis Plan

Patients

Patients aged 18–80 years with pathologically confirmed head and neck cancer receiving radical or postoperative radiotherapy and Karnofsky score greater than 80 points were eligible for recruitment. Patients who received radiotherapy only, radiotherapy concurrent with single-drug platinum chemotherapy, or induction chemotherapy with fewer than three cycles were eligible. Patients with a history of head and neck radiotherapy, distant metastases, and targeted drug or non-platinum drug chemotherapy during radiotherapy were excluded.

Treatments

All patients received 20 g Kanglaite (200 mL) daily, administered as an intravenous injection for 5 days a week, concurrently with radiotherapy. Kanglaite injection was used before or after radiotherapy, no time interval requirement between Kanglaite and radiotherapy. The dosage of radiotherapy was adjusted as follows: 70 Gy for gross tumors and positive lymph nodes, 66 Gy for tumor bed (operation bed), 60 Gy for high-risk lymph node drainage area, and 50 Gy for low-risk lymph node drainage area. Single fraction dose was 1.82–2.12 Gy for 5 days a week, once a day. Intensity-modulated radiation therapy was used and the radiotherapy planning system used was Eclipse 7.0. Recombinant human granulocyte colony-stimulating factor and antibiotics were not allowed as prophylactic treatments. After the final patient completed radiotherapy and observation data was recorded, the trial stopped.

Study end-points

Primary end-point was the incidence of radiation-induced mucositis. Secondary end-points were as follows: (i) blood toxicity, liver and kidney functions, and other toxic events; (ii) nutritional status, overall QOL, and QOL specifically related to head and neck.

All the end-points could be observed in the course of radiotherapy; therefore, long-term follow-up data may be reported in the future. After radiotherapy, patients

were evaluated for recurrence, metastases, and death every 3 months in the first 3 years, and every 6 months thereafter until death.

Evaluation of data

Acute toxicity indicators

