Mucositis and the associated symptoms (manifested as pain, dysphagia, or dry mouth), blood cell count, liver and kidney functions, and other toxic events were assessed at baseline (before radiotherapy), every week during radiotherapy, and post radiotherapy. All adverse events were graded according to NCI Common Terminology Criteria for Adverse Events v4.0 (NCI-CTCAE4.0).

Mucositis in patients with head and neck cancer receiving radiotherapy usually occurs in the oral cavity, oropharynx, hypopharynx, and larynx. In NCI CTCAE4.0, grade 1 oral mucositis, pharyngeal mucositis, and laryngeal mucositis are defined as those causing mild discomfort in normal oral intake, requiring no intervention. Grade 2 mucositis is defined as that causing moderate pain, not interfering with oral intake, but altering oral intake. Grade 3 mucositis is defined as that causing severe pain, with severely altered eating/swallowing, requiring medical intervention. Grade 4 mucositis is defined as that with life-threatening consequences, requiring urgent intervention. Grade 5 mucositis is defined as that causing death.

Blood cell count, liver and kidney functions were assessed at baseline (before radiotherapy)—via blood test—every week during radiotherapy, and post radiotherapy. The lowest scores during radiotherapy were recorded and considered as data.

Nutritional status

Nutritional status was scored using the Patient-Generated Subjective Global Assessment (PG-SGA). The scores 0–1 is well-nourished or anabolic, scores 2–8 is suspected or moderate under-nutrition, score ≥ 9 is severely undernourished. The PG-SGA scores were recorded at baseline (before radiotherapy), every week during radiotherapy, and post radiotherapy. The highest PG-SGA scores recorded every week during the course of radiotherapy were used as the data obtained during

radiotherapy.

Therapeutic nutritional supports were provided based on the grade of dysphagia. Nutritional supports were divided into oro-enteral nutrition preparation, tube feeding, total parenteral nutrition, and separated nutrition infusion. Total parenteral nutrition was defined as a combination of amino acids, carbohydrates, and fats administered intravenously. Separate nutrition infusion was defined as intravenous administration of any one amino acid, carbohydrate, and fat. Nutritional treatment was not considered for those receiving nutritional treatment for less than 3 days or <10 kcal/kg per day.

Quality of life score

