European Organization for Research and Treatment of Cancer (EORTC) QLQ-C30 questionnaire was used to evaluate the overall QOL. European Organization for Research and Treatment of Cancer QLQ-Head and Neck 35 (EORTC QLQ-H&N35) questionnaire was used to evaluate QOL specific for head and neck. Quality of life for each patient was assessed at baseline (before radiotherapy), every week during radiotherapy, and post radiotherapy using the EORTC QLQ-C30 and EORTC QLQ-H&N35 questionnaires. The QLQ-C30 and QLQ-H&N35 questionnaires were distributed to patients weekly during radiotherapy, and the lowest scores were recorded as data during radiotherapy. Using the EORTC Group scoring guidelines, each item of the QLQ-C30 and QLQ-H&N35 questionnaires was scored from 0 to 100. Higher scores for functions in QLQ-C30 implied a better quality of life; higher scores for the symptoms in QLQ-C30 and all items in QLQ-H&N35 indicated worsening quality of life.

Statistical analysis

Descriptive statistics were used to summarize patient baseline characteristics. Normally distributed data are reported as mean and standard deviation. Qualitative data are presented as number of observations and percentages. All statistical analyses were conducted using SPSS Statistics v. 18 (IBM Corporation, NY, USA). A two-tailed $p < 0.05$ was considered statistically significant.

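### The on-treatment value for PG-SGA, quality of life and laboratory tests is the extreme of about 6–8 weekly readings, so comparing it with single-reading periods mixes artefact with change

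*Combined protocol and SAP*

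**What the plan says.** Under Nutritional status, three assessment periods are set: "The PG-SGA scores were recorded at baseline (before radiotherapy), every week during radiotherapy, and post radiotherapy". The weekly series is then collapsed: "The highest PG-SGA scores recorded every week during the course of radiotherapy were used as the data obtained during" radiotherapy. A high PG-SGA is bad ("score ≥ 9 is severely undernourished"), so for this scale the rule does pick the worst week.

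Under Acute toxicity indicators, blood counts and liver and kidney function follow the same three-period schedule, with the rule "The lowest scores during radiotherapy were recorded and considered as data". Under Quality of life score, both questionnaires are given weekly and "the lowest scores were recorded as data during radiotherapy". That section also sets the direction of the scales: "Higher scores for functions in QLQ-C30 implied a better quality of life", whereas "higher scores for the symptoms in QLQ-C30 and all items in QLQ-H&N35 indicated worsening quality of life".

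No extreme-value rule is given for baseline or post radiotherapy. The number of post-radiotherapy readings is not stated. Statistical analysis offers descriptive summaries and a two-tailed 0.05 threshold; it names no test, no comparison between periods and no sample size. Study end-points lists all these measures as secondary. Treatments describes a single arm.

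**The concern.** The extreme of several noisy readings lies beyond a single reading by construction. The during-radiotherapy value is therefore not on the same footing as the values on either side of it. This is a different matter from whether highest or lowest is the right choice for a given scale: PG-SGA already takes its worst value, and the problem remains.

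The plan presents the extreme as the on-treatment datum itself, not as an additional peak-toxicity figure. There is no control arm carrying the same artefact against which it could cancel. Beside baseline, the shift can be read as an effect of treatment; beside post radiotherapy, as a reversal. For the scales where the lowest score is the best week, the rule would mask toxicity, in a trial whose purpose is to study toxicity.

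Two further consequences follow. A patient who stops early or misses assessments contributes fewer readings and so a less extreme value. In a multi-scale questionnaire, the extremes may come from different weeks, giving a profile the patient never had at one time.

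**Working it through.** The plan gives no figure to reproduce. The correlations, SDs and sample sizes below are assumptions.

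**1. Number of weekly readings (k).** From Treatments: 70 Gy (gross tumour) or 66 Gy (tumour bed), 1.82–2.12 Gy per fraction, five fractions a week. Weeks = dose ÷ fraction size ÷ 5.
- 70 ÷ 2.12 = 33.0 fractions, 6.6 weeks; 70 ÷ 1.82 = 38.5 fractions, 7.7 weeks.
- 66 ÷ 2.12 = 31.1 fractions, 6.2 weeks; 66 ÷ 1.82 = 36.3 fractions, 7.3 weeks.
- Both fraction limits fit a 33-fraction plan: 33 × 2.12 = 69.96 Gy and 33 × 1.82 = 60.06 Gy, that is 6.6 weeks.

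So k is about 6–8.

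**2. Shift with no true change.** Take exchangeable normal readings with within-patient correlation r. In units of the between-patient SD at one visit, shift = √(1 − r) × E[max of k standard normals]. By numerical integration, E[max] is 1.27, 1.35 and 1.42 for k = 6, 7 and 8.

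| r | √(1 − r) | k = 6 | k = 7 | k = 8 |
|---|---|---|---|---|
| 0.5 | 0.707 | 0.90 | 0.96 | 1.01 |
| 0.8 | 0.447 | 0.57 | 0.60 | 0.64 |
| 0.9 | 0.316 | 0.40 | 0.43 | 0.45 |

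The shift from the extreme back to one post-radiotherapy reading is equal and opposite. The chance that the extreme lies beyond both single readings is k/(k + 2): 6/8 = 75% to 8/10 = 80%. A patient with only four readings has E[max] = 1.03 instead of 1.35 at k = 7.

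**3. Effect on a paired test, if one were used.** The factor √(1 − r) appears in both the mean and the SD of the paired difference, so it cancels. For k = 7 the variance of the maximum is 0.392, and the standardised difference is 1.352 ÷ √(1 + 0.392) = 1.15 at any r below 1. At an assumed n = 20 the expected t is about 1.15 × √20 = 5.1, against a critical value of 2.09. Simulated rejection with no true change is 99–100% for n = 20–60 and k = 6–8. Under AR(1) correlation of 0.8–0.9 (n = 40, k = 7) the shift is 0.62–0.84 SD and rejection is still about 100%.

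**4. Illustrations.** On a 0–100 scale with an assumed SD of 20 and k = 7, the shift is 0.96 × 20 = 19 points at r = 0.5 and 0.52 × 20 = 10 points at r = 0.85. For PG-SGA with an assumed mean of 5 and SD of 3 (normal scores rounded to whole numbers), the share at 9 or above is 12% at a single visit. By the maximum it is 37–42% at r = 0.5 and 26–29% at r = 0.8.

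**5. If patients truly worsen.** Simulated linear rise over seven weekly readings, with the excess of the worst week over the true last-week change, in SD:

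| True rise | r = 0.5 | r = 0.7 | r = 0.85 |
|---|---|---|---|
| none | 0.96 | 0.74 | 0.52 |
| 1 SD | 0.62 | 0.42 | 0.24 |
| 2 SD | 0.42 | 0.26 | 0.13 |

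**6. Direction.**
- PG-SGA (highest = worst), QLQ-C30 function and blood counts (lowest = worst): false deterioration, then recovery.
- QLQ-C30 symptoms and all QLQ-H&N35 items (lowest = best week, read literally): with no true change, false improvement then worsening, of the same size.
- Liver and kidney markers that rise with damage: the same reversal may apply. The markers are not listed, so this is conditional.

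**7. Alternative summary.** With one fixed week or the mean of the weekly readings, the no-change shift is within 0.01 SD of zero and the paired test rejects in about 5% of simulations (4–6%).

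**The case against.** The strongest reply is that the plan contains no comparison to be biased. Its statistics are descriptive, no paired test or change from baseline is named, and a worst-on-treatment value is a legitimate account of peak toxicity. That stands as far as it goes. The rejection rate is conditional on a test the plan does not specify, and a single post-radiotherapy reading is inferred from the schedule. It does not dispose of the point, because means or percentages for three periods set side by side invite the same misreading without any test.

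It is also fair that no change is the case in which the artefact is largest. Some worsening during radiotherapy is likely, and the excess then shrinks (step 5). With a true 1 SD rise, r = 0.7 and n = 20, a fixed last-week test would reject in more than 99.9% of trials anyway. The extreme would then inflate the size of the change, not reverse the conclusion.

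A reader might infer that every one of these measures shows spurious deterioration and recovery. The stated direction of QLQ-C30 symptoms and QLQ-H&N35 rules that out. A reader might also infer that an artefactual recovery will be credited to the product. No text in the plan does so, and overstated deterioration in a single arm would count against it. Nor do these summary rules touch the primary end-point.

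**Conclusion.** The concern holds in conditional form. Only the on-treatment period is reduced to an extreme, so a comparison with baseline or post radiotherapy would be partly artefact. The shift is about 1.0 to 0.4 SD with no true change (r = 0.5 to 0.9), and about 0.6 to 0.2 SD beyond the true last-week change with a 1 SD rise (r = 0.5 to 0.85). A no-change paired test against baseline would reject in over 99% of trials of 20–50 patients. These sizes rest on normal readings and on assumed correlations and sample size. The mechanism does not depend on those values; it would vanish only if a patient's readings did not vary at all.

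The direction differs by scale, and for symptom and head-and-neck items, taken literally, it would mask toxicity. The documents do not support the stronger claims that the plan specifies a biased test or that the mucositis result is compromised. This is a cheap improvement to secondary end-points that should be made.

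**What to change.** Report PG-SGA, each QLQ-C30 and QLQ-H&N35 scale and each laboratory test at the scheduled time points: baseline, each treatment week, post radiotherapy. Base any change from baseline on one week named in advance (for example the last week of radiotherapy) or on a repeated-measures analysis of the weekly values.

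Keep the worst value, in the correct direction for each scale, only as a descriptive worst-on-treatment figure. Show the number of readings behind it, and do not compare it with single-reading periods. State how many post-radiotherapy readings are taken.

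The weekly assessments are already scheduled, so no visits are added. The plan should say that every weekly value is kept, because its wording leaves open whether only the extreme is recorded. The downside is longer tables and less extreme on-treatment values.

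### The lowest-score rule for quality of life during radiotherapy, read literally, keeps the least-affected week on every scale where a higher score is worse

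*Combined protocol and SAP*

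**What the plan says.** Under Study end-points, the secondary end-points include "nutritional status, overall QOL, and QOL specifically related to head and neck". Under Quality of life score, the schedule is: "Quality of life for each patient was assessed at baseline (before radiotherapy), every week during radiotherapy, and post radiotherapy". The weekly forms completed during treatment are then reduced by one rule that covers both the QLQ-C30 and the QLQ-H&N35: "the lowest scores were recorded as data during radiotherapy".

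The same paragraph gives the range, "each item of the QLQ-C30 and QLQ-H&N35 questionnaires was scored from 0 to 100", and two opposite directions: "Higher scores for functions in QLQ-C30 implied a better quality of life", but "higher scores for the symptoms in QLQ-C30 and all items in QLQ-H&N35 indicated worsening quality of life". No exception by scale type and no reversed scoring is written.

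Under Nutritional status, the PG-SGA is also a scale on which a higher score is worse. There the plan keeps the other extreme: "The highest PG-SGA scores recorded every week during the course of radiotherapy were used".

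**The concern.** A minimum means different things on scales that run in opposite directions. On a QLQ-C30 function scale it is the patient's worst week. On a QLQ-C30 symptom scale or any QLQ-H&N35 scale it is the week in which the patient was least affected. An analyst who follows the sentence would record the mildest symptom week as the result for the whole course of radiotherapy.

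This concerns the during-radiotherapy value of the entire head-and-neck instrument and of all QLQ-C30 symptom scales, and so both named quality-of-life end-points. Those values could not be compared with the function scales or the PG-SGA, which are kept at their worst. All patients receive Kanglaite and no concurrent control is described, so no comparison arm would share and expose the bias. In a trial about reducing toxicity, the error makes symptoms look milder.

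**Working it through.** The document gives no quality-of-life figure to reproduce. The check is one of logic, followed by an illustration of size.

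**Step 1: apply the rule to the stated directions.**

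| Measure | Higher score means | Value kept | Week selected |
|---|---|---|---|
| QLQ-C30 functions | better | lowest | worst |
| QLQ-C30 symptoms | worse | lowest | least affected |
| QLQ-H&N35, all items | worse | lowest | least affected |
| PG-SGA | worse | highest | worst |

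The minimum of a set of weekly scores cannot exceed any of them. Where higher is worse, it therefore understates the peak whenever the weekly scores differ. This needs no assumption. For example, take a baseline of 10 and weekly symptom scores of 10, 20, 35, 50, 60, 70, 75 (assumed). The rule records 10, a change of 10 − 10 = 0. The worst week is 75, a change of 75 − 10 = +65.

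**Step 2: number of weekly forms.** Under Treatments: "Single fraction dose was 1.82–2.12 Gy for 5 days a week, once a day". Taking 66 to 70 Gy and the extremes of fraction size:
- 66 / 2.12 = 31.1, rounded up to 32 fractions; 32 / 5 = 6.4 weeks.
- 70 / 1.82 = 38.5, rounded up to 39 fractions; 39 / 5 = 7.8 weeks.

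This gives about 6 to 8 forms. The plan does not pair total doses with fraction sizes, so this is an outer range. 70 / 2.12 = 33.0 fractions (6.6 weeks) lies inside it.

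**Step 3: size, by simulation.** All score inputs are assumptions: baseline mean 20, peak mean 60, between-patient SD 15, within-patient SD 8 or 12, scores limited to 0–100, 6, 7 or 8 forms, and 200,000 patients per setting. The minimum and maximum are taken scale by scale. Each range covers the form counts and both within-patient SDs.

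| True course | Mean change, lowest score | Mean change, highest score | Largest weekly mean change | Recorded value at or below baseline (lowest score) |
|---|---|---|---|---|
| Linear, first form at baseline mean | −5.5 to −1.7 | +40.8 to +44.6 | +38.4 to +38.9 | 60–70% |
| Linear, equal steps from week 1 | −2.0 to +3.9 | +41.3 to +45.2 | +38.3 to +39.0 | 36–59% |
| Early rise (40, 50, then 60) | +13.6 to +17.5 | +47.2 to +53.4 | +38.4 to +39.0 | 5–17% |
| No change | −13.3 to −8.6 | +9.3 to +15.6 | 0.0 to +0.1 | not needed |

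The weekly means fall slightly short of +40 because scores are limited at 0.

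The shortfall is the largest weekly mean change minus the lowest-score change, setting by setting. For the linear courses it runs from 39.0 − 3.9 = 35.1 to 38.4 + 5.5 = 43.9 points. For the early rise it runs from 39.0 − 17.5 = 21.5 to 38.4 − 13.6 = 24.8, or about 21 to 25 allowing for rounding.

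The last row shows that both extremes are biased against a single baseline form when nothing changes. The lowest score shows a false improvement and the highest a false worsening. Weekly means show neither.

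**The case against.** The strongest reply is that *lowest* is loose wording for *worst quality of life*. The PG-SGA rule shows that worst-value logic was used elsewhere. Under Acute toxicity indicators, the plan also speaks of the lowest scores for blood counts and liver and kidney function together, which reads like a stock phrase. This is a fair possibility, and it means that biased data have not been shown. It does not repair the text. For the PG-SGA the plan matched the word to the direction of the scale; here it did not, and an analyst cannot tell what to extract.

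The sentence could also mean that one lowest week per patient was kept, so that symptom scores would come from a bad week. But no such week is written, and it is undefined across scales that run in opposite directions.

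On size, the peak-week mean is a demanding comparator. Against the average over the whole course, the same simulation gives shortfalls of about 19 to 24 points (linear) and 16 to 21 (early rise), which are smaller but in the same direction. The plan also specifies no change-from-baseline analysis for quality of life, so that contrast is the review's own. It is also true that these are secondary end-points and that a highest-score rule has its own noise bias. The latter is why the fix includes means by week.

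**Conclusion.** The concern holds. As written, the rule selects the least-affected week for the QLQ-C30 symptom scales and all QLQ-H&N35 scales and so understates deterioration there. That conclusion rests only on the rule and the scale directions in the same paragraph. The point values rest on assumed scores and on scale-by-scale minima, and should be read as an illustration. Whether the reported data are affected cannot be known from the document.

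Not affected: quality of life at baseline and after radiotherapy, the QLQ-C30 function scales, the weekly CTCAE grading of pain, dysphagia and dry mouth, and the primary mucositis endpoint. This should be fixed, because it is a wrong rule for a named secondary end-point.

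**What to change.** - Replace the sentence with a rule by direction, applied scale by scale: the lowest weekly score for QLQ-C30 function scales and global health, and the highest for QLQ-C30 symptom scales and all QLQ-H&N35 scales. State the direction of global health, which the plan omits.
- Check which values were actually extracted. If they were the literal minima, re-derive the affected scales from the weekly forms.
- Report mean score and change from baseline by week for every scale, since a worst-week value set against one baseline form is pushed upward by noise.

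The cost is one sentence, a data check, some derivation and one table, with no extra patients or visits. The document does not say that every weekly score was retained. Where only the lowest was kept, the affected scales cannot be re-derived and this must be stated as a limitation. If the literal rule was used, the corrected symptom scores will look less favourable.
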